#### **5.13.6.1. Abnormal Hepatic Tests**

Analyses for abnormal hepatic tests will involve 4 laboratory analytes: ALT, AST, total bilirubin, and ALP. In addition to the analyses described in Section 5.13.3, this section describes specific analyses for this topic.

The central laboratory reference ranges (CLRM reference ranges) will be used for these laboratory assessments (ALT, AST, total bilirubin, and ALP).

Analyses for change from baseline to last observation, change from the baseline value to the minimum value during the Induction/Maintenance Period, change from the baseline value to the maximum value during the Induction/Maintenance Period, and treatment-emergent high or low laboratory results at any time are described in Section 6.13.3.

The patients with the following abnormal elevations in hepatic laboratory tests at any time will be listed for both the Induction and Maintenance periods:

- ALT measurement  $\geq 3$  times,  $\geq 5$  times and  $\geq 10$  times the central laboratory ULN.
- AST measurement  $\geq 3$  times,  $\geq 5$  times and  $\geq 10$  times the central laboratory ULN.
- Total bilirubin measurement  $\geq 2$  times the central laboratory ULN.
- ALP measurement  $\geq 1.5$  times the central laboratory ULN.

#### **5.13.6.2. Renal Function Effects**

Effects on renal function will be assessed through analysis of elevated creatinine.

The CTCAE will be applied for laboratory tests related to renal effects (Table FCAB.6.4 Common Terminology Criteria for Adverse Events (CTCAE) Related to Renal Effects 4). This CTCAE grading scheme is consistent with both Version 3.0 and Version 4.03 of the CTCAE guidelines.

Shift tables will show the number and percentage of subjects from baseline to maximum during the Induction and Maintenance Periods, with baseline depicted by highest grade during the baseline period. A shift table summary displaying the number and percentage of subjects with

maximum postbaseline results will be presented by treatment group within the following categories:

- Decreased; postbaseline category < baseline category
- Increased; postbaseline category > baseline category
- Same; postbaseline category = baseline category.

Treatment-emergent lab abnormalities related to elevated creatinine occurring at any time during the Dosing Period will be tabulated using the CTCAE grades shown in [Table FCAB.6.4](#)

Common Terminology Criteria for Adverse Events (CTCAE) Related to Renal Effects

. Planned and unplanned measurements will be included.

Treatment-emergence will be characterized using 5 criteria:

- any increase in postbaseline CTCAE grade from worst baseline grade
- increase to Grade 1 or above at worst postbaseline
- increase to Grade 2 or above at worst postbaseline
- increase to Grade 3 or above at worst postbaseline
- increase to Grade 4 at worst postbaseline.

**Table FCAB.6.4      Common Terminology Criteria for Adverse Events (CTCAE) Related to Renal Effects**

| Lab Test            | CTCAE Version | Grade      | Criteria in SI or CN Units                  |
|---------------------|---------------|------------|---|
| Elevated creatinine | 3.0           | 0 (normal) | $\leq$ ULN                                  |
|                     |               | 1          | $>$ ULN and $\leq$ 1.5 $\times$ ULN         |
|                     |               | 2          | >1.5 $\times$ ULN and $\leq$ 3 $\times$ ULN |
|                     |               | 3          | >3 $\times$ ULN and $\leq$ 6 $\times$ ULN   |
|                     |               | 4          | >6 $\times$ ULN                             |

Abbreviations: CN = conventional (US); CTCAE = Common Terminology Criteria for Adverse Events; SI = Système International; ULN = upper limit of normal.

### 5.13.6.3. Infections

Infections will be defined using the PTs from the MedDRA Infections and Infestations SOC, with additional terms from the Investigations SOC being used in selected instances, as described below.

Treatment-emergent infections will be analyzed according to various groups of infectious events including:

- all infections
  - all PTs in the Infections and Infestations SOC,
- serious infections
  - all PTs in the Infections and Infestations SOC that are SAEs,
- infections that require therapeutic intervention (antibiotics, antivirals, antifungals, and so on)
  - all PTs in the Infections and Infestations SOC for which there is an antimicrobial concomitant medication associated with that event for that subject,

- herpes zoster
  - specific Lilly-defined PTs from the Herpes Viral Infections high-level term (HLT) in the Infections and Infestations SOC, shown in [Appendix 1](#),
- tuberculosis
  - specific Lilly-defined PTs from the Tuberculous Infections HLT and the Investigations SOC, shown in [Appendix 2](#)
- viral hepatitis
  - all PTs from the Hepatitis Viral Infections HLT (HLT code 10057212) in the Infections and Infestations SOC.

For each infection event, the frequency for each PT will be provided, ordered by decreasing frequency in the LY3375880 highest dose group by infection group: all infections, serious infections (overall and on each approach to identifying SAEs), infections that require therapeutic intervention, herpes zoster infections, tuberculosis, and viral hepatitis.

In addition to the incidence of infectious AEs by MedDRA PT as described above, the number and percentage of subjects with treatment-emergent infectious AEs by treatment group will be summarized and listed.

#### Potential Opportunistic Infections:

Potential opportunistic infections (POIs) will be identified according to 2 different approaches.

POIs are identified from TEAEs based on a Lilly-defined list of MedDRA PTs, shown in the [Appendix 3](#). These PTs are a subset of terms from the Infections and Infestations SOC.

For the POIs identified from MedDRA PTs, the number and percentage of subjects overall and for each specific PT will be summarized by treatment group, with specific event terms ordered by decreasing frequency in the LY3375880 highest dose.

#### Association of Infections with Lymphopenia or Neutropenia:

The relationship between the occurrence of lymphopenia and neutropenia with the occurrence of infections will be evaluated based on case reviews. Inferential analyses and/or graphical displays may be conducted if warranted. Infection outcomes considered for this analysis are any infection, any serious infection, infections that require therapeutic intervention (antibiotics, antivirals, antifungals, and so on), tuberculosis, herpes zoster, and viral hepatitis.

#### **5.13.6.4. Allergic Reactions/Hypersensitivities**

A search will be performed using the current MedDRA version 20.0 SMQs to search for relevant events, using the following queries:

- Anaphylactic reaction SMQ (20000021)
- Hypersensitivity SMQ (20000214)
- Angioedema SMQ (20000024)

Events that satisfy the queries will be listed, by temporal order within patient ID, and will include SOC, PT, SMQ event categorization including detail on the scope (narrow or broad), reported AE term, AE onset and end dates, severity, seriousness, outcome, etc.

### **5.13.6.5. Columbia Suicide Severity Rating Scale**

Suicidal ideation, suicidal behavior, and self-injurious behavior without suicidal intent, based on the C-SSRS, will be listed by patient and visit. Only patients that show suicidal ideation/behavior or self-injurious behavior without suicidal intent will be displayed (ie, if a patient's answers are all 'no' for the C-SSRS, then that patient will not be displayed). However, if a patient reported any suicidal ideation/ behavior or self-injurious behavior without suicidal intent at any time point then all their ideation and behavior will be displayed, even if not positive.

#### **5.13.6.5.1. Self-Harm Supplement Form and Self-Harm Follow-up Form**

The Self-Harm Supplement Form is a single question to enter the number of suicidal behavior events, possible suicide behaviors, or nonsuicidal self-injurious behaviors. If the number of behavioral events is greater than zero, it will lead to the completion of the Self-Harm Follow-Up Form. The Self-Harm Follow-Up Form is a series of questions that provides a more detailed description of the behavior cases. A listing of the responses give on the Self-Harm Follow-Up Form will be provided.

## **5.14. Subgroup Analyses**

Subgroup analyses comparing each dose of LY3375880 to placebo will be performed on the ITT population at Week 16 for the following:

- Proportion of patients achieving IGA 0 or 1 with a 2-point improvement
- Proportion of patients achieving EASI75 Response Rate
- Proportion of patients achieving Itch NRS 4-point improvement

The following subgroups (but not necessarily limited to only these) will be categorized into disease-related characteristics and demographic characteristics will be evaluated:

- Patient Demographic and Characteristics Subgroups:
  - Gender (male, female)
  - Age group (<65,  $\geq$ 65)
  - Diagnosis age group (<18 years,  $\geq$ 18 years)
  - Baseline weight: ( $\leq$  median,  $>$  median)
  - Race: (American Indian or Alaska Native, Asian, Black or African American, Native Hawaiian or Other Pacific Islander, White, Multiple)
  - Region: Japan vs. Rest of World
  - Immunoglobulin E (IgE): intrinsic(<200 kU/I) or extrinsic ( $\geq$ 200 kU/I)
  - Baseline allergen-specific IgE: Positive ( $\geq$  0.35 kU/L) vs Negative ( $<$  0.35 kU/L)
  - IL-19 Concentration: High ( $\geq$  21 ng/L) vs. Low ( $<$  21 ng/L)
  - Periostin: High ( $\geq$  19 ng/mL) vs. Low ( $<$  19 ng/mL)
  - TARC: High ( $\geq$  70 pg/mL) vs. Low ( $<$  70 pg/mL)

- IL-13: High ( $\geq 0.7$  pg/mL) vs. Low ( $< 0.7$  pg/mL)
- Previous and Concomitant Therapy Subgroups:
  - Prior use of TCNI (yes, no)
  - Prior systemic therapy use (yes, no)
- Baseline Disease-Related Characteristics Subgroup
  - Duration of AD from diagnosis (0 to  $<2$  years, 2 to  $<5$  years,  $\geq 5$  to  $<10$  years,  $\geq 10$  to  $<20$  years,  $\geq 20$  years)
  - Baseline disease severity (IGA score): 3, 4
  - Baseline EASI: ( $\leq$  median,  $>$  median)
  - Baseline BSA: ( $\leq$  median,  $>$  median)

Descriptive statistics will be provided for each treatment and stratum of a subgroup as outlined, regardless of sample size. The subgroup analyses for categorical outcomes will be performed using logistic regression. The model will include the categorical outcome as the dependent variable and treatment, subgroup, and treatment-by-subgroup interaction as explanatory variables. Missing data will be imputed using NRI (Section 5.4.1). The treatment-by-subgroup interaction comparing treatment groups will be tested at the 0.1 significance level. The p-value from the logistic regression model will be reported for the interaction test. Response counts and percentages will be summarized by treatment for each subgroup category. The difference in percentages and 100(1-alpha)% confidence interval (CI) of the difference in percentages using the Newcombe-Wilson without continuity correction will be reported. The p-value from the Fisher's exact test will also be produced.

Additional subgroup analyses on efficacy may be performed as deemed appropriate and necessary.

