6.1. Inclusion Criteria

Informed Consent

- [1] Are at least 18 years of age at the time of informed consent.

Note: Use local requirements to provide consent if the age of adulthood is defined as >18 years.

- [2] Are able to read, understand, and give documented informed consent.

Disease Characteristics

- [3] Have a diagnosis of AD at least 12 months prior to screening, as defined by the American Academy of Dermatology: Guidelines of care for the management of AD; Section 1. Diagnosis and assessment of AD (see [Appendix 6](#)).
- [4] Have moderate-to-severe AD, including all of the following:
 - a. Eczema Area and Severity Index (EASI) score ≥ 16 at randomization (Visit 2).
 - b. IGA score of ≥ 3 at randomization (Visit 2).
 - c. $\geq 10\%$ of body surface area (BSA) involvement at randomization (Visit 2).
- [5] Have a documented history provided by a physician and/or investigator of inadequate response to existing topical medications within 6 months preceding screening, or history of intolerance to topical therapy as defined by at least 1 of the following:
 - a. Inability to achieve good disease control defined as mild disease or better (e.g., IGA ≤ 2) after use of at least a medium-potency topical corticosteroid (TCS) for at least 4 weeks, or for the maximum duration recommended by the product prescribing information (e.g., 14 days for super-potent TCS), whichever is shorter. Topical corticosteroids may be used with or without topical calcineurin inhibitors (TCNIs).

- b. Subjects who failed systemic therapies intended to treat AD within 6 months preceding screening, such as cyclosporine, methotrexate (MTX), azathioprine, and mycophenolate mofetil (MMF), will also be considered as a surrogate for having inadequate response to topical therapy.
- c. Documented history of clinically significant adverse reactions with the use of TCS such as skin atrophy, allergic reactions, and systemic effects that in the opinion of the investigator outweigh the benefits of retreatment.

[6] Have applied emollients daily for at least 14 days prior to randomization and agree to use emollients daily throughout the treatment period.

[7] Are willing and able to undergo punch biopsies according to the Schedule of Activities (Section 2).

Other Subject Characteristics

[8] **Women of childbearing potential:**

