Sporothrix schenckii
Other invasive fungi: Mucormycosis (zygomycosis) (Rhizopus , Mucor , and Lichtheimia), Scedosporium/Pseudallescheria boydii , Fusarium
Protozoan
Leishmaniasis (visceral only)
Microsporidiosis
Toxoplasmosis
Trypanosoma cruzi infection (Chagas disease) (disseminated disease only)

This table is provided to aid the investigator in recognizing infections that may be considered opportunistic in the context of biologic therapy, for the purposes of Exclusion Criterion [22]. This list is not exhaustive. Investigators should use their clinical judgment, as well as discussion with the Lilly-designated medical monitor, in determining if other infections may be considered opportunistic, for the purposes of Exclusion Criterion [22]. Consider tuberculosis (TB) and non-TB mycobacterial disease to be opportunistic infections in the context of biologic therapy. See Section 6.2 for the approach to screening for latent TB infection within the study. Subjects with any history of **active** TB are excluded from the study, regardless of previous or current TB treatments.

Source: Adapted from Winthrop et al. (2015).

Appendix 6. American Academy of Dermatology: Criteria for the Diagnosis and Assessment of Atopic Dermatitis

Features to be considered in diagnosis of subjects with AD:

Essential Features—Must be present:

- pruritus
- eczema (acute, subacute, chronic)
 - typical morphology and age-specific patterns*
 - chronic or relapsing history

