### **5.2.1. Analysis Populations**

**Enrolled population:** The enrolled population is defined as all participants who sign informed consent.

**Intent-to-treat (ITT) population:** The ITT population analysis set is defined as all randomized patients, even if the patient does not take the assigned treatment, does not receive the correct treatment, or otherwise does not follow the protocol.

**Per-Protocol (PPS) population:** The PPS populations is defined as all randomized patients who do not commit an Important Protocol Deviation (IPD) that could potentially compromise efficacy results.

**Safety population:** The safety population is defined as all randomized patients who receive at least 1 dose of their assigned double-blind study treatment..

**Maintenance Period Population:** All ITT patients who received at least one dose of study treatment and have entered the maintenance period at Week 16 (Visit 8).

Unless otherwise specified, the efficacy and health outcome analyses will be conducted on the ITT population (Gillings and Koch 1991), which seeks to preserve the benefits of randomization and avoid the issue of selection bias. Patients will be analyzed according to the treatment to which they were randomized.

Safety analyses will be done on the safety population. Patients will be analyzed according to the dosing regimen to which they were assigned. Analyses of the safety endpoints, many of which are incidence based, will include all patients in the safety population, unless specifically stated otherwise.

In the rare situation where a patient is Lost to Follow-up at the first postbaseline visit, but some safety data exists (eg, unscheduled laboratory assessments) after first dose of study drug, a listing of the data or a patient profile will be provided.

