### **5.2.2. Definition of Baseline and Postbaseline Measures**

The baseline value for the efficacy and health outcomes for the Induction and Maintenance Periods is defined as the last non-missing measurement on or prior to the date of first study drug administration (expected at Week 0, Visit 2). The baseline value for the daily diary assessments (Itch NRS, Skin Pain NRS) is defined as the average of the non-missing assessments in the last 7 days prior to the date of first study drug administration (expected at Week 0, Visit 2). Criteria for derivation of the weekly average requires that there must be at least 4 non-missing measurements in the 7 days indicated, otherwise, an expanded window of 14 days prior to first study drug administration, if available, may be utilized in order to obtain the most recent 4 non-missing measurements prior to first study drug administration (ie, Day -14 to Day -1). If there are not at least 4 non-missing assessments collected prior to the date of first study drug

administration using the aforementioned method, then the baseline will be designated as missing. Other definitions of baseline value, such as the last measurement on or prior to rescue, may be used to conduct additional supporting analyses.

Postbaseline measurements are collected after study drug administration through Week 60 (Visit 801) or early discontinuation visit. For data collected in the electronic Clinical Outcomes Assessment (eCOA) tablet (including Patient-Reported Outcomes [PRO] and Clinician-Reported Outcomes [ClinRO]) and related to efficacy assessments, unscheduled postbaseline visits that fall within the visit windows defined by Lilly will be summarized in the by-visit analyses if there is no scheduled visit available. That is, a  $\pm 2$  day window is applied to Visit 3 (Week 1), Visit 4 (Week 2), and Visit 5 (Week 4), and a  $\pm 4$  day window is applied to Visit 6 (Week 8), Visit 7 (Week 12), and Visit 8 (Week 16), as well as to every visit in the Maintenance Period. If there is more than 1 unscheduled visit within the defined visit window and no scheduled visit is available, the unscheduled visit closest to the scheduled visit date will be used.

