|         | 
The SCORing Atopic Dermatitis (SCORAD) index uses the rule of nines to assess disease extent (head and neck 9%; upper limbs 9% each; lower limbs 18% each; anterior trunk 18%; back 18%; and genitals 1%). It evaluates 6 clinical characteristics to determine disease severity: (1) erythema, (2) edema/papulation, (3) oozing/crusts, (4) excoriation, (5) lichenification, and (6) dryness on a scale of 0 to 3 (0=absence, 1=mild, 2=moderate, 3=severe). The SCORAD index also assesses subjective symptoms of pruritus and sleep loss in the last 72 hours on visual analogue scales (VAS) of 0 to 10 where 0 is no itch or sleep loss and 10 is worst imaginable itch or sleep loss. These 3 aspects: extent of disease, disease severity, and subjective symptoms combine to give a maximum possible score of 103 (Stalder et al. 1993; Kunz et al. 1997; Schram et al. 2012).
 | 
 
▪ SCORAD75
 
▪ SCORAD90
 
 | 
% Improvement in baseline <math>\geq 75\%</math>:
 % change from baseline <math>\leq 75</math>
 
% Improvement in baseline <math>\geq 90\%</math>:
 % change from baseline <math>\leq 90</math>
 | 
Missing if baseline or observed value is missing.
 
Missing if baseline or observed value is missing.
 |

| Measure                              | Description   | Variable                                | Derivation / Comment   | Imputation Approach if with Missing Components   |
|--------------------------------------|---|---|--|--|
| Itch Numeric Rating Scale (NRS)      | The Itch Numeric Rating Scale (NRS) is a patient-administered, 11-point horizontal scale anchored at 0 and 10, with 0 representing “no itch” and 10 representing “worst itch imaginable.” Overall severity of a patient’s itching is indicated by selecting the number that best describes the worst level of itching in the past 24 hours (Naegeli et al. 2015; Kimball et al. 2016). Refer to Section 5.2.2 for details on how to calculate the weekly score which will be used in the continuous analysis. | ▪ Itch NRS score                        | Single item; range 0-10. Refer to Section 5.2.2 on how to derive the visit score.    | Refer to Section 5.2.2 on how to derive the visit score.   |

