| Itch NRS                               | • Itch NRS score
• Change from baseline in Itch NRS score             | MMRM                            | ITT; PPS  | LY3375880 600-mg or LY3375880 150-mg or LY3375880 50-mg vs PBO; Week 16 | Exploratory Analysis |
|  | • Proportion of patients with at least a 4-point improvement in Itch NRS | Logistic regression using NRI   | ITT; PPS (those with baseline Itch NRS of 4 or greater) | LY3375880 600-mg or LY3375880 150-mg or LY3375880 50-mg vs PBO; Week 16 | Exploratory Analysis |
| Skin Pain Numeric Rating Scale (NRS)   | • Skin Pain NRS score
• Change from baseline in Skin Pain NRS score   | MMRM                            | ITT; PPS  | LY3375880 600-mg or LY3375880 150-mg or LY3375880 50-mg vs PBO; Week 16 | Exploratory Analysis |
| Patient-Oriented Eczema Measure (POEM) | • POEM score
• Change from baseline in POEM score                     | MMRM                            | ITT   | LY3375880 600-mg or LY3375880 150-mg or LY3375880 50-mg vs PBO; Week 16 | Exploratory Analysis |
| Dermatology Life Quality Index (DLQI)  | • DLQI total score
• Change from baseline in DLQI                     | MMRM                            | ITT   | LY3375880 600-mg or LY3375880 150-mg or LY3375880 50-mg vs PBO; Week 16 | Exploratory Analysis |

Abbreviations: ITT = intent-to-treat; MMRM = mixed model repeated measures; NRI = nonresponder imputation; NRS = Numeric Rating Scale; PBO = placebo; PPS = per protocol set.

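### SAP 5.14 runs the Itch NRS 4-point responder subgroups on all randomised patients, while Table FCAB.5.2 restricts the same endpoint to a baseline Itch NRS of at least 4

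*SAP*

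**What the plan says.** - **Subgroup analyses (SAP 5.14).** "Subgroup analyses comparing each dose of LY3375880 to placebo will be performed on the ITT population at Week 16". The third endpoint listed is "Proportion of patients achieving Itch NRS 4-point improvement". Neither the list nor the modelling text after it sets a baseline itch level or refers to Table FCAB.5.2.
- **ITT (SAP 5.2.1).** "The ITT population analysis set is defined as all randomized patients, even if the patient does not take the assigned treatment".
- **Main itch responder analysis (SAP 5.11, Table FCAB.5.2).** The population entry for the 4-point responder at Week 16 is "ITT; PPS (those with baseline Itch NRS of 4 or greater", where the bracket closes. The analysis is labelled exploratory.
- **Derivations (SAP Table FCAB.5.1).** Itch has a visit score and a change from baseline. There is no derivation of the 4-point responder that could carry the restriction into 5.14.
- **Scale and baseline.** The Itch NRS is "Single item; range 0-10". Its baseline (SAP 5.2.2) "is defined as the average of the non-missing assessments in the last 7 days prior to the date of first study drug administration", so fractional values below 4 can occur.
- **Entry (Protocol 6.1, criterion 4).** "Have moderate-to-severe AD, including all of the following": EASI at least 16, IGA at least 3 and BSA at least 10%. No Itch NRS threshold appears. Protocol Appendix 6 lists pruritus under "Essential Features—Must be present", without a score.
- **Status (Protocol 10.2.7.2).** Subgroup analyses are planned for the primary IGA endpoint, are not powered, and are exploratory.

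**The concern.** The SAP names two populations for one endpoint at one time point. The table's restriction shows that its authors saw the need for a denominator of patients able to respond; 5.14 does not carry it over.

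A programmer who follows 5.14 as written will produce subgroup tables whose counts do not add up to the overall itch responder table. Every patient with a baseline below 4 becomes a certain nonresponder in whichever arm and stratum he or she falls. Response percentages and risk differences, which 5.14 reports for each subgroup category, are pulled towards zero.

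At stake is the consistency and readability of an exploratory display. If patients with low itch were more common in one stratum than another (IGA 3 against 4, or below against above the median EASI), the dilution would also differ between strata.

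**Working it through.** **The plan's own figure.** The documents give no rate or power for the itch responder. The one stated power, at least 90% for the primary IGA endpoint (36% against 8%, 50 per arm, 2-sided Fisher's exact test at 0.05), reproduces as 91.4% by full enumeration. This point does not touch it.

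**Step 1: can a patient below 4 respond?** Response needs baseline minus Week 16 score to be at least 4. The Week 16 score, being an average of values from 0 to 10, is never below 0. With a baseline b below 4 the largest possible improvement is b, so response is impossible even with complete data.

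**Step 2: dilution.** Let f be the share with baseline below 4, and p_D and p_P the response rates among those at 4 or above on drug and placebo. On the unrestricted ITT population, with f equal across arms:

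- rate = (1 − f) × p
- risk difference = (1 − f) × (p_D − p_P)

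Neither f nor any itch response rate is in the documents, so all values below are assumed. The 36% and 8% are borrowed from the IGA assumption for illustration only.

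| Assumed p_D, p_P | f = 0 | f = 5% | f = 20% | f = 30% |
|---|---|---|---|---|
| 45%, 15% | 30.0 points | 28.5 | 24.0 | 21.0 |
| 36%, 8% | 28.0 points | 26.6 | 22.4 | 19.6 |
| 50%, 20% | 30.0 points | 28.5 | 24.0 | 21.0 |

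**Step 3: unequal f between strata.** Take 45% and 15% in both IGA strata, with f = 20% in IGA 3 and 5% in IGA 4.

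- IGA 3: 36% against 12%, difference 24.0 points, odds ratio (0.36/0.64)/(0.12/0.88) = 4.13.
- IGA 4: 42.75% against 14.25%, difference 28.5 points, odds ratio (0.4275/0.5725)/(0.1425/0.8575) = 4.49.
- Artefact: 28.5 − 24.0 = 4.5 points, or about 0.085 on the log odds ratio scale (log of 4.49/4.13, before rounding).

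**Step 4: is that visible at this sample size?** Assume each arm of 50 splits 25/25 by IGA.

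- Standard error of the difference between the two risk differences: √[(0.12×0.88 + 0.36×0.64 + 0.1425×0.8575 + 0.4275×0.5725)/25] = 0.168, or 16.8 points, against an artefact of 4.5.
- Standard error of the log odds ratio difference: square root of the sum of 1/[25p(1 − p)] over the same four rates = 1.02, against 0.085.
- A simulated Wald interaction test (one dose against placebo, 0.5 added to each cell, level 0.10) rejects in about 7.5% of trials under the unrestricted rule and about 7.5% under the restriction. A harsher case (50% and 20%, f = 5% against 30%) gives about 9%, still below the nominal 10%.

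**Step 5: does restricting lose power?** Fisher power for one dose against placebo with 36% and 8% among eligible patients:

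| f | Unrestricted, 50 per arm | Restricted (n per arm) |
|---|---|---|
| 5% | 89.3% | 89.9% (48) |
| 10% | 86.7% | 87.3% (45) |
| 20% | 80.1% | 83.7% (40) |
| 30% | 71.6% | 76.6% (35) |

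In these cases the smaller denominator costs no power, because the patients removed cannot respond in either arm.

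**The case against.** The best defence is that 5.14 lists its endpoints in shorthand. SAP 5.11 says Table FCAB.5.2 supplies the analysis population, so ITT in 5.14 may only mean ITT rather than the per-protocol set, with the table's restriction carried over. That reading is reasonable and may be what was intended. But 5.14 names its population, does not cite the table, and has no responder derivation to fall back on. The literal reading is equally available and gives different numbers.

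It is also fair to say that f is unknown and could be small in patients with moderate-to-severe disease for whom pruritus is a diagnostic requirement. The floor applies to every randomised arm, so it dilutes and in expectation favours none. Both points stand and limit the size of the problem, but they do not settle which denominator is to be used.

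Three stronger readings are tempting and not supported:

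- **False effect modification.** A reader might infer that the subgroup results will show it. Nothing in the documents says that f differs between strata, and Step 4 shows that even an assumed gap is lost in the noise.
- **Nonresponder imputation as the cause.** SAP 5.4.1 applies it to missing data, discontinuation of study drug and rescue. Patients with a low baseline fail by scale arithmetic, whatever the imputation.
- **The bracket in Table FCAB.5.2 covering only the per-protocol set.** The position of the bracket allows this, but it would mean restricting the supportive set and leaving the main set unrestricted for the same floor, which is unlikely to be meant.

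**Conclusion.** The inconsistency is real and minor. Taken literally, SAP 5.14 includes patients who cannot meet the itch endpoint, and it conflicts with Table FCAB.5.2 on the population for that endpoint. The certain consequence is that the rule does not match the one for the overall itch table; the denominators differ whenever anyone is randomised with a baseline below 4. The conditional consequence is dilution of subgroup rates and risk differences by (1 − f): 1.5 points of a 30-point difference at f = 5%, and 6 points at f = 20%. These sizes rest on assumed response rates and on an f that the documents do not give.

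Apparent differences between subgroups caused by unequal f remain hypothetical and would probably be small against sampling error. The itch responder and all subgroup analyses are exploratory. The primary analysis, its power and the sample size are unaffected.

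**What to change.** In SAP 5.14, restate the third endpoint as: *at least a 4-point improvement in Itch NRS, among ITT patients with baseline Itch NRS ≥ 4*. This matches Table FCAB.5.2.

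Two optional clarifications: reword the table entry to *ITT and PPS, each restricted to baseline Itch NRS ≥ 4*, and add the 4-point responder, with its baseline condition, to Table FCAB.5.1.

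The cost is a line of SAP text and slightly smaller subgroup denominators. The filter is already needed for the main itch analysis, and no data collection changes.
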